2.2.2 Secondary Objectives

The following secondary objectives will be assessed 6 months after initiating treatment with telotristat ethyl (XERMELO):

- To estimate the proportion of patients reporting satisfaction of CS-related diarrhea control
- To estimate the proportion of patients reporting satisfaction of CS-related flushing control
- To estimate the proportion of patients reporting reduction in rescue SSA use

- To estimate the proportion of patients reporting reduction in the dose of long-acting SSA injection
- To estimate the proportion of patients reporting reduction in the frequency of long-acting SSA injection
- To estimate the proportion of patients reporting an overall improvement in CS control after initiating XERMELO based on the Patient Global Impression of Change (PGIC)
- To estimate the proportion of patients who had reduction in work-related absenteeism, presenteeism, activity impairment, and overall productivity loss after initiating XERMELO based on Work Productivity and Activity Impairment Questionnaire: Specific Health Problem v.2.0 (WPAI-SHP)
- To estimate the proportion of patients reporting weight gain

2.2.3 *Exploratory Objectives*

To explore the association between satisfaction with overall and CS symptom control (ie, diarrhea, flushing) at month 6 and long-term health outcomes such as, CS-related hospitalization, CS-related emergency room (ER) visits, and mortality over the study period

2.3 Study Endpoints

2.3.1 *Primary Endpoint*

The primary endpoint of the study is the proportion of patients with CS who are satisfied with their overall symptom control, 6 months after initiating treatment with telotristat ethyl (XERMELO).

2.3.2 *Secondary Endpoints*

The following secondary endpoints will be assessed 6 months after initiating treatment with telotristat ethyl (XERMELO):

- The proportion of patients reporting satisfaction of CS-related diarrhea control
- The proportion of patients reporting satisfaction of CS-related flushing control
- The proportion of patients reporting reduction in rescue SSA use
- The proportion of patients reporting reduction in the dose of long-acting SSA injection
- The proportion of patients reporting reduction in the frequency of long-acting SSA injection
- The proportion of patients reporting an overall improvement in CS control after initiating XERMELO based on PGIC

- The proportions of patients who had reduction in work-related absenteeism, presenteeism, activity impairment, and overall productivity loss after initiating XERMELO based on the WPAI-SHP
- The proportion of patients reporting weight gain

2.3.3 *Other Endpoints*

Other endpoints include incidence of CS-related hospitalizations, incidence of CS-related emergency room (ER) visits, and incidence of mortality at 6-month intervals for up to 3 years after initiation of treatment with XERMELO.

Another endpoint, not described in the protocol, is the proportion of patients with a reduction in the number of bowel movements. This endpoint will be assessed at the 6-month Follow-up after initiation of treatment with XERMELO.

2.4 Sample Size Determination

The sample size was derived by satisfying design assumptions for the primary study endpoint of the proportion of patients with CS who are satisfied with their overall symptom control, 6 months after initiating treatment with telotristat ethyl (XERMELO). Of specific interest is the proportion of patients with CS who are at least somewhat satisfied with their control of CS at 6 months, defined as those patients with a response of either "very satisfied" or "somewhat satisfied". This proportion will be estimated as x/n , where x is the number of patients in the study who are either "Very satisfied" or "Somewhat satisfied", and n is the number of patients with a non-missing response for the primary endpoint. Two-sided 95% confidence limits (CLs) will be calculated for this proportion using normal approximation. The true proportion may be approximately 50%; hence, an expected proportion of 50% was used in the sample size calculation as it requires the largest n . It is desired for the proportion to be known with a precision, ω , of 5%, that is, for the CLs to be $(x/n) \pm \omega$. Based on the expected proportion of 50% and the precision requirement of 5%, $n = 385$ patients are needed to have a non-missing response for the primary endpoint. Assuming that 40% of the patients who participate in the study will drop out prior to the 6-month survey, then a minimum of $N = 643$ patients, with CS who initiate treatment with XERMELO, should be entered into the study.

3 DATA SOURCES AND VARIABLES

3.1 Data Sources

Data will be collected from patients electronically using web-based questionnaires. Patients who enroll in the study will complete a Baseline questionnaire within 30 days of enrollment and up to 6 Follow-up questionnaires at 6-month intervals after Baseline.

Prescription fill data, type of insurance, and reasons for discontinuation, including mortality, will be collected directly from the specialty pharmacy using a process that is still being determined and will be described in a separate document.

3.2 Variables for Analysis

3.2.1 *Demographics, Medical History, and Change in Weight*

Several demographic and medical history variables will be collected as part of the Baseline questionnaire. These include:

- Age and sex
- Highest level of education
- Race and ethnicity
- Geographic region
- Height (in feet and inches) and weight (in pounds)
- Diagnosis date for CS
- Site and diagnosis date of primary NET causing CS

Patients will also be asked to qualitatively assess their weight change since initiating XERMELO at each 6-month Follow-up ("I weigh less," "I weigh about the same," "I weigh more," "I don't know").

3.2.2 *Prior and Concomitant Treatments for Carcinoid Syndrome*

Patients' use of other treatments for CS, specified below, will be assessed at Baseline and/or at each 6-month Follow-up:

- Recent or concomitant use of short-acting or long-acting somatostatin analog medications at Baseline
- Changes in SSA use (frequency and dose) at each Follow-up
- NET-related surgery for CS within 6 months of Baseline and the reason for the surgery

- Additional concomitant treatments for CS (radionuclide therapy, radiation, chemotherapy, embolization, chemoembolization directly into liver)

3.2.3 Symptom Control

Satisfaction with control of diarrhea, flushing, and overall CS symptoms will be assessed at Baseline. Satisfaction with how XERMELO has controlled diarrhea, flushing, and overall CS symptoms will be assessed at the initial 6-month Follow-up only. The questionnaire items allow patients to choose a response on a 5-level Likert scale ranging from "Very dissatisfied" (level 1) to "Very satisfied" (level 5). For the assessments of satisfaction with control of diarrhea and flushing, "Not applicable" (level 0) is also 1 of the response options, for those patients who do not have the symptom that is being assessed.

At the initial 6-month Follow-up, patients will also be asked to assess the change in the number of bowel movements on a 7-level Likert scale from "A great deal worse" to "A great deal better." This assessment is not described in the study protocol.

3.2.4 Patient Global Impression of Change

At the initial 6-month Follow-up, patients will be asked to rank their impression of their CS symptoms on a 7-level Likert scale from "Very much worse" to "Very much improved."

3.2.5 Work Productivity and Activity Impairment Questionnaire—Specific Health Problem (WPAI-SHP)

The WPAI-SHP is a self-administered questionnaire ([Reilly et al., 1993](#)) comprising 6 questions that measure the effect of health problems on participants' ability to work and participate in regular activities based on their experiences in the previous 7 days. This questionnaire will be administered at Baseline and at the initial 6-month Follow-up.

The WPAI-SHP includes 4 domains (absenteeism, presenteeism, work productivity loss, and activity impairment). All participants will be asked whether they are employed (Q1) and how their CS-related problems affected their regular activities (Q6). Employed participants will be asked about hours of work missed due to CS-related problems (Q2), hours of work missed for any reason (eg, vacation, holidays, time off to participate in this study) (Q3), hours actually worked (Q4), and the degree that CS affected their productivity while working (Q5). An integer scale from 0 to 10 is used for Q5 and Q6, where 0 corresponds to no effect and 10 corresponds to complete effect.

Responses to the items are scored to produce the following 4 domains:

- Absenteeism: work time missed due to CS = [REDACTED]
- Presenteeism: impairment while working due to CS = [REDACTED]

- Work productivity loss: overall work impairment due to CS = [REDACTED]
[REDACTED]
- Activity impairment: activity impairment due to CS = [REDACTED]

Each score is then multiplied by 100 to express domains in terms of impairment percentages, with higher numbers indicating greater impairment and less productivity (ie, worse outcomes).

3.2.6 *Carcinoid Syndrome-related Health Care Resource Utilization*

At Baseline and at each Follow-up, questionnaire items will ask patients about ER visits and hospitalizations during the prior 6-month period. Data collected will include the following:

- The number of ER visits and the CS-related reason for each visit
- The number of hospitalizations, the number of nights for each stay, and the CS-related reason for each hospitalization

3.2.7 *Study Discontinuation and Mortality*

Patients will be terminated from the study if they discontinue the use of XERMELO, withdraw consent for participation, or are lost to follow-up. Information on reasons for discontinuation will be provided by the specialty pharmacy.

Information on patient deaths during the study will be collected by the specialty pharmacy and transferred to RTI-HS for analysis. This information may be aggregated (ie, counts of patients who die during each 6-month interval) or patient-level, with or without actual dates of death.

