5.1.1 Survey Conduct

An electronic consent and survey questionnaire approved by an Institutional Review Board (IRB) will be used by RTI to program the online survey for the purpose of standardizing responses among patients.

Each patient will complete up to 7 web-based surveys over the duration of the study. Each survey is anticipated to take no more than 20 minutes on average.

All assessments, except mortality, will be patient-reported; medical records will not routinely be requested or reviewed as part of this observational study unless required for safety reporting purposes. As patient recall over time may be limited, partial responses as in the case of dates of onset, and/or estimates of numerical information will be accepted.

Participation in the study is contingent on continued use of XERMELO. Each survey will establish ongoing treatment with XERMELO and continued consent to study participation prior to subsequent data collection.

The initial survey is intended to gather Baseline information, which may include:

- Sociodemographics (age, year of birth, sex, race, ethnicity, education, geographic region)
- Current medical history as it relates to CS, NET burden, NET location, and related conditions
 - Location of NET
 - Date of diagnosis; CS and NET
 - CS-related hospitalization(s)
 - CS-related ER visit(s)
 - NET-related surgery (eg, tumor debulking, lysis of adhesions)
- Satisfaction with CS, CS-related diarrhea and/or flushing control prior to starting XERMELO, where applicable
- Height and weight
- Concomitant medication as it relates to the following:
 - Long-acting SSA therapy

- Use of rescue medication - short-acting SSA
- Systemic tumor-directed therapy
- Liver-directed therapy (eg, chemoembolization)
- WPAI-SHP

The initial survey should be completed no later than 30 days, and subsequent surveys should be completed no later than 14 days, after the unique survey link has been provided to the patient via e-mail. Patients will be asked to complete a survey every 6 months for up to 3 years. The following patient-reported data may be collected as described in [Appendix A](#):

- Satisfaction with CS, CS-related diarrhea and/or flushing control after initiating XERMELO, where applicable
- PGIC
- Concomitant medication as it relates to the following:
 - Change in use of rescue medication - short-acting SSA
 - Change in long-acting SSA therapy
 - Systemic tumor-directed therapy
 - Liver-directed therapy (eg, chemoembolization)

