8.2.1.6 Incidence of CS-related Hospitalizations and Emergency Room (ER) Visit

The incidence of CS- related hospitalization and/or ER visits will be collected at Baseline and at each of the subsequent time points. Patients will be asked to provide additional information, including but not limited to the date(s), reason for each CS-related hospitalization or ER visit, action taken, outcome, dosage, and dose regimen of XERMELO.

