2 STUDY DESIGN AND OBJECTIVES

2.1 Study Design

This observational, noninterventional, single-arm study will include adult patients with CS who are initiating XERMELO as a new treatment. A minimum of 643 patients are expected to enroll.

A specialty pharmacy tasked with distributing XERMELO to patients will be responsible for the identification and recruitment of patients, and all eligible patients who are initiating treatment with XERMELO will be invited to participate in this study. Patients who enroll will be asked to complete up to 7 longitudinal, web-based surveys, including a Baseline assessment at enrollment, and a Follow-up survey every 6 months for up to 3 years. The Baseline questionnaire may be completed any time within a 30-day window following the electronic mail invitation to a patient to participate in the survey. The Follow-up surveys at 6-month intervals may be completed at any time within a \pm 14-day window.

Prescription fill data, type of insurance, and reasons for discontinuation, including mortality, will be collected directly from the specialty pharmacy using a process that is still being determined and will be described in a separate document.

A full description of the study design is found in the study protocol dated 19 May 2017 (Lexicon Pharmaceuticals, Inc.).

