5 STATISTICAL ANALYSIS

5.1 Statistical Methods

5.1.1 General Considerations

Derivation of analytic variables will be detailed in a separate analytic variable specification document to be produced in Microsoft Excel. This document will be developed at the time of the first interim analysis and will be maintained through the final analysis. It will be provided to Lexicon at the end of the study, along with the corresponding SAS data sets.

All analyses will be descriptive in nature. For continuous and ordinal variables, the number of available observations, means, standard deviations (SDs), medians, minimums, and maximums will be provided. For categorical variables, the frequency and percentage in each category will be displayed. For computation of percentages, missing values and "Prefer not to answer" responses will not be included in the denominator. Results will be presented by study time point, where applicable. Additionally, all questionnaire data will be displayed in listings. Height and weight information will be collected in feet and inches and in pounds but will be summarized in the tables in centimeters and kilograms, respectively. By convention, dates will be displayed in DDMMYYYY format (eg, 17JAN2017). For the times since diagnosis of CS and diagnosis of primary NET and all time-to-event analyses, the date of Baseline questionnaire completion will be considered as Day 1, and times will be expressed in months or years, as appropriate. The day before the date of Baseline questionnaire completion will be considered Day -1; there will be no Day 0.

All analyses will be performed in SAS, Version 9.4 or higher (SAS Institute, Cary, NC).

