5.1.5 Other Endpoint Analyses

5.1.5.1 Analyses of Incidence of Emergency Room Visits, Hospitalizations, and Mortality

Incidence proportions for patients with at least 1 ER visit, at least 1 hospitalization, and mortality during each 6-month Follow-up interval will be reported along with 95% CLs. The denominator for each incidence proportion will be the number of patients enrolled in the

study at the beginning of that particular 6-month interval who also provide a non-missing response to the questionnaire item for each type of event.

The time to the first occurrence of a CS-related ER visit, time to the first occurrence of a CS-related hospitalization, time to the first occurrence of a CS-related ER visit or hospitalization, and time to mortality will be analyzed using the nonparametric Turnbull estimation method ([Turnbull, 1976](#)) for interval-censored data available in SAS PROC ICLIFETEST for each 6-month interval during Follow-up. These tables will display the number of patients still at risk at the beginning of the interval along with the number of events and censored observations within each interval. Estimates of the survival probability (the proportion of patients without the event) will be provided for the upper boundary of each interval, and these probabilities will also be displayed as figures. Estimated quartiles for event-free time (with 95% CLs) will be reported.

If death dates are available for the analysis of mortality, this analysis will be performed using the Kaplan-Meier method instead of the Turnbull method. Estimated quartiles for survival time (with 95% CLs) will be reported, and estimated survival probabilities will be displayed as Kaplan-Meier curves.

Details for all ER visits and hospitalizations, including the reason for the visit or hospitalization, will be provided in data listings.

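### A fixed 6-month recall for ER visits and hospitalizations does not join end to end when surveys can move by ±14 days, and the SAP states no rule for assigning or de-duplicating the events

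*SAP*

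**What the plan says.** - **Recall.** SAP 3.2.6, for Baseline and each Follow-up: "questionnaire items will ask patients about ER visits and hospitalizations during the prior 6-month period". It lists the number of events, the reasons and, for hospital stays, the nights. It does not list event dates.
- **Completion window.** SAP 2.1: "The Follow-up surveys at 6-month intervals may be completed at any time within a" ±14-day window; Protocol Appendix A gives the same tolerance. Protocol 5.1.1 words it differently: "subsequent surveys should be completed no later than 14 days, after the unique survey link has been provided". It does not say when the link is sent relative to the due date.
- **Baseline timing.** SAP 2.1: "The Baseline questionnaire may be completed any time within a 30-day window following the electronic mail invitation".
- **Schedule and time origin.** SAP 3.1 plans "up to 6 Follow-up questionnaires at 6-month intervals after Baseline". SAP 5.1.1 says that for "all time-to-event analyses, the date of Baseline questionnaire completion will be considered as Day 1". Protocol Appendix A labels Baseline as Day 1 with a tolerance of +30 days, which leaves open whether the later due dates run from the invitation or from completion.
- **Analysis.** SAP 5.1.5.1 reports, per 6-month interval, the proportion of patients with one or more events. Time to first event "will be analyzed using the nonparametric Turnbull estimation method". Protocol 10.4.1 counts events after Baseline.
- **Dates.** Protocol 8.2.1.6: "Patients will be asked to provide additional information, including but not limited to the date(s), reason for each CS-related hospitalization or ER visit". Protocol 5.1.1 accepts partial dates. The Protocol Synopsis describes the follow-up surveys as collecting new occurrences.

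**The concern.** A look-back of fixed length that ends on a movable date cannot tile follow-up. Three things can go wrong:

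- If two consecutive surveys are more than 6 months apart, some days are never asked about, and a visit on those days is missed.
- If they are less than 6 months apart, some days are asked about twice, and one visit can make the patient a case in two intervals.
- If the month-6 survey falls less than 6 months after Baseline completion, its recall reaches before Day 1. A visit already reported at Baseline can then become the first follow-up event.

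SAP 5.1.5.1 gives no rule for any of these. The analyses exposed are the interval incidence of ER visits and hospitalizations, time to first event, and the exploratory association of these outcomes with month-6 satisfaction (SAP 2.2.3 and 5.1.5.4). Double counting matters only for the per-interval proportions and counts. Whole-study occurrence of at least one event and time to first event are exposed to gaps and to pre-Baseline visits, not to duplicates.

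**Working it through.** The documents give no figure for recall gaps or overlaps, so there is none to reproduce. Inputs: recall 6 months, taken as 183 days (SAP 3.2.6); Follow-up window ±14 days (SAP 2.1, Protocol Appendix A) or 0 to +14 days if the link goes out on the due date (one reading of Protocol 5.1.1); Baseline completed 0 to 30 days after invitation (SAP 2.1).

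**1. Consecutive Follow-ups.** Let the completion offsets be a, then b. Spacing is 183 + (b − a).
- With ±14 days, spacing runs from 183 − 28 = 155 to 183 + 28 = 211 days. Maximum gap or overlap is 28 days, and 28/183 = 15.3% of an interval.
- If offsets are independent and uniform (assumption), the mean gap is 28/6 = 4.7 days and the mean overlap is the same; 4.67/183 = 2.6% each.
- With 0 to +14 days, the maximum is 14 days and the mean 14/6 = 2.3 days of each.

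**2. Month 6 against Day 1 (Baseline completion).**

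| Due date counted from | Window | Maximum reach before Day 1 | Maximum days after Day 1 not asked about |
|---|---|---|---|
| Baseline completion | ±14 | 14 | 14 |
| Baseline completion | 0 to +14 | 0 | 14 |
| Invitation | ±14 | 14 + 30 = 44 | 14 |
| Invitation | 0 to +14 | 30 | 14 |

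Mean days before Day 1 and mean days missed, with uniform timing: 14/4 = 3.5 and 3.5 in the first row; 0 and 14/2 = 7 in the second; 15.5 and 0.5 in the third (simulation of 200,000 patients).

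**3. Chance that an event falls there.** The documents give no event rate. Assume that a share p of 5% to 30% of patients has an event per 6 months, with constant hazard. The chance of an event in d days is 1 − (1 − p)^(d/183).

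| p | d = 28 (extreme) | Averaged over uniform ±14 completion |
|---|---|---|
| 5% | 0.8% | 0.13% |
| 10% | 1.6% | 0.27% |
| 20% | 3.4% | 0.57% |
| 30% | 5.3% | 0.90% |

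The averaged figures apply per pair of surveys, to the overlap and equally to the gap.

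**4. Net effect on interval incidence.** Under a constant hazard a 183-day look-back returns p. Compare that with the incidence over the actual time between surveys.
- Due dates from Baseline completion, ±14 days: 20.0% reported against 20.0% true. Gaps and overlaps cancel.
- Due dates from the invitation, ±14 days, month 6: 20.0% reported against 18.5% true from Baseline to survey (5% against 4.6%, 10% against 9.2%, 30% against 27.9%). This runs in one direction.
- Due dates from Baseline completion, 0 to +14 days, month 6: 20.0% against 20.7%, a small understatement, because 7 days on average are not asked about.

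**5. With a recall that starts at the previous survey**, gap, overlap and reach before Day 1 are all 0 days by construction.

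**The case against.** The case against is substantial. The questionnaire is not in the documents; SAP 3.2.6 only describes it, and the Synopsis speaks of new occurrences, which may discourage repeat reports. Protocol 8.2.1.6 collects dates. SAP 5.1.1 leaves derivations to a separate specification, and an interval-censored estimator can take patient-specific bounds. The 28-day figure needs opposite extremes in consecutive surveys. The endpoints are classed as other or exploratory, and the analyses are descriptive.

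Most of this stands, and it rules out three stronger readings that a reader might infer:

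- *That events are in fact missed or counted twice.* The documents show only that they can be.
- *That the dates are ignored.* The SAP is silent on them, and naming Turnbull does not settle it.
- *That pre-treatment visits inflate early on-treatment incidence.* Reach before Day 1 depends on early completion or on the scheduling anchor. Days before Baseline completion are not necessarily off treatment, since nothing ties completion to the first dose. No data in the documents show that visits cluster before the drug is started.

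One may also object that excluding visits before Baseline completion could discard events after treatment began, since Protocol 10.3.2 and SAP 2.3.3 define incidence from treatment initiation. That is largely answered: Protocol 10.4.1 counts events after Baseline, and SAP 5.1.1 sets Baseline completion as Day 1.

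What the objection does not remove is that the stated recall and window do not join end to end and no rule covers the result. Dates would resolve duplicates and pre-Baseline visits, but not visits on days never asked about, and they may be partial.

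**Conclusion.** The point holds as a minor improvement. As written, recall can leave up to 28 days uncovered or doubly covered between consecutive Follow-ups (14 days if completion is 0 to +14), averaging about 4.7 days of each under uniform ±14 completion. Reach before Day 1 at month 6 is 0 to 44 days, depending on a scheduling anchor that the documents do not settle. With constant hazard, the average effect on interval incidence is small and largely cancels. The main exception is scheduling from the invitation: 20.0% against 18.5% at month 6, for an assumed 20% rate. The primary and secondary endpoints and the sample size are unaffected, and so is mortality, which comes from the specialty pharmacy. The event rates and the uniform completion pattern are assumptions.

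**What to change.** 1. Word the Follow-up item as *since your last survey on [auto-filled date]*; at month 6, since the Baseline survey date.
2. Add the event dates to SAP 3.2.6, in line with Protocol 8.2.1.6.
3. In SAP 5.1.5.1, state that events are assigned to intervals by reported date; that events before Day 1 (Baseline completion) are excluded; that a visit already reported in a previous survey is removed; and that the actual previous and current survey dates are the interval bounds when a date is missing or partial.

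The cost is one auto-filled date in a web survey, one added variable and a few sentences in the SAP. The downside is that surveys completed before the change can use only the date-based rule, which cannot recover visits that fell in a gap.
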